3.2.4.3 Clinical Laboratory and Pregnancy Test

- Hematology panel (complete blood count with differential, ANC, and platelet count): at Screening, Cycle 1 (weekly prior to dosing if on dosing day, Day 3. Note: Does not need to be performed prior to C1/D1, if performed during screening \leq 7 days from C1/D1), each cycle thereafter (Day 1 and 15 prior to dosing), EOT, 1M FUP, and as clinically indicated.

PAREXEL International
Statistical Analysis Plan Template for Early Phase Studies

Symphogen A/S
Sym013-01

- Biochemistry panel (sodium, potassium, chloride, bicarbonate or carbon dioxide, blood urea nitrogen (BUN), creatinine, glucose, bilirubin [total and direct], AST, ALT, ALP, calcium, magnesium, phosphorus, albumin, total protein, uric acid, amylase, lipase, and creatine kinase): at Screening, Cycle 1 (weekly prior to dosing if on dosing days, Day 3. Note: Does not need to be performed prior to C1/D1, if performed during screening \leq 7 days from C1/D1), each cycle thereafter (Day 1 and 15 prior to dosing), EOT, 1M FUP, and as clinically indicated.
- Coagulation panel (PT, PTT and INR): at Screening, Cycle 1 (Day 1 and 15 prior to dosing. Note: Does not need to be performed prior to C1/D1, if performed during screening \leq 7 days from C1/D1), each cycle thereafter (Day 1 prior to dosing), EOT, 1M FUP, and as clinically indicated.
- Urinalysis (specific gravity, pH, protein, glucose, ketones, occult blood, leukocyte esterase, nitrite, bilirubin, and urobilinogen): at Screening, Cycle 1 (Day 1 and 15 prior to dosing. Note: Does not need to be performed prior to C1/D1, if performed during screening \leq 7 days from C1/D1), each cycle thereafter (Day 1 prior to dosing), EOT, 1M FUP, and as clinically indicated.
- Pregnancy test (serum human Chorionic Gonadotropin (β -hCG) at screening, urine β -hCG thereafter, in women of childbearing potential): at Screening, EOT and as clinically indicated.

3.2.4.4 Electrocardiogram

A 12-lead ECG will be performed on Screening, EOT, and as clinically indicated.

Parameters measured will include heart rate, PR, R-R, QRS, QT, and QTc intervals (calculated by the Fridericia [QTcF] or Bazzett's [QTcB] correction formula). Clinical assessment (abnormality as clinically significant or not clinically significant) will be performed.

3.2.4.5 Echocardiogram (ECHO) or Multi-Gated Acquisition (MUGA) Scan

Transthoracic echocardiogram (ECHO) or Multi-Gated Acquisition (MUGA) scan will be performed at Screening, EOT, and as clinically indicated.

PAREXEL International
Statistical Analysis Plan Template for Early Phase Studies

Symphogen A/S

Sym013-01

3.2.4.6 Vital Signs and Body Measurements

Vital signs, including temperature, heart rate, blood pressure, and body weight will be monitored at Screening, prior to each dosing, EOT, 1-month FUP and as clinically indicated.

3.2.4.7 Physical Examination

Full physical examination at Screening to include evaluation of: general appearance, skin, head, ears, eyes, nose, throat, neck/thyroid, chest/breasts, lungs, cardiovascular system, abdomen, musculoskeletal system, pulses, lymph nodes, neurologic status and mental status.

Thereafter, a targeted physical examination may be performed as indicated: at Screening, Day 1 of each cycle prior to dosing, EOT, 1M FUP and as clinically indicated.

3.2.4.8 Eastern Cooperative Oncology Group (ECOG) performance Status (PS) score

ECOG PS will be assessed at Screening, Day 1 of each cycle (prior to dosing), EOT, 1M FUP and as clinically indicated.

ECOG PS Score:

- 0=Fully active, able to carry on all pre-disease activities without restrictions
- 1=Restricted in physically strenuous activity but ambulatory and able to carry out work of a light or sedentary nature e.g., light housework, office work
- 2=Ambulatory and capable of self-care, but unable to carry out any work activities. Up and about more than 50% of waking hours
- 3=Capable of only limited self-care, confined to bed or chair more than 50% of waking hours
- 4=Completely disabled. Cannot carry on self-care. Totally confined to bed or chair
- 5=Dead

PAREXEL International
Statistical Analysis Plan Template for Early Phase Studies

Symphogen A/S
Sym013-01

4 STATISTICAL METHODS

4.1 Data Quality Assurance

All tables, figures and data listings to be included in the report will be independently checked for consistency, integrity and in accordance with standard PAREXEL procedures.

4.2 General Presentation Considerations

Baseline

‘Baseline’ is defined as the last available pre-treatment assessment, considering both scheduled and unscheduled assessments.

Safety assessments at Cycle 1 Day 1 with no time of assessment (i.e. Vital Signs and Body Measurements, ECOG PS, Physical Examination) are assumed to be taken pre-treatment.

End of Treatment (EOT)

‘End of Treatment’ is defined as the first assessment on or after the last dose of study treatment, considering both scheduled and unscheduled assessments.

Unscheduled assessments

Unscheduled assessments will be presented in listings in chronological order.

Post Baseline unscheduled assessments (for Clinical Laboratory, ECG QTc, etc.) will be used for determination of worst result (i.e. Maximum and Minimum post Baseline result) as well as the maximal laboratory CTCAE grade if applicable; also, all post baseline tumor evaluation assessments will be used to derive BOR.

Except considered as Baseline, EOT or worst result, unscheduled assessments will not be included in summaries.

PAREXEL International
Statistical Analysis Plan Template for Early Phase Studies

Symphogen A/S
Sym013-01

Treatment Day

‘Treatment Day’ will be calculated relative to the date of C1/D1 as follow:

- assessments taken before the first infusion of IMP

Treatment Day = Assessment Date - First IMP infusion Date

- assessments after the first infusion of IMP

Treatment Day = Assessment Date - First IMP infusion Date + 1.

Missing Data

In case of partially missing date of birth or date of diagnosis, the following rule will be applied: if year and months are known but day is missing, then the day will be imputed as 15th; in case of only year known, the day and month will be imputed as 15th June.

Specific rules for handling for missing efficacy assessments are detailed in section 4.10.1.3.

Methods for handling missing concomitant medication and adverse events dates are detailed in sections 4.8 and 3.2.4.2 respectively.

Imputations will be used to derive parameters, in listings original data will be presented as collected.

Data Listing

All original and derived parameters for all consented patients will be listed.

All listings will include scheduled and unscheduled measurements.

Unless specified otherwise, data in listings will be presented by dose regimen (Q1W or Q2W), dose group, patient, and visit (ordered by date and time within patient).

All listings will display the same number of decimals as in the source data. All raw data will be reported exactly as provided.

Quantitative derived variables (e.g. Duration of Response, Time to Progression, Actual Treatment duration) will be shown with 1 decimal place (d.p.) precision.

PAREXEL International
Statistical Analysis Plan Template for Early Phase Studies

Symphegen A/S
Sym013-01

The data for the patients who consented but for any reason did not receive any dose of study drug (including screening failures) will be also listed but with a label of '*' and a footnote to flag these.

Efficacy, Exposure and PK/PD Data Listing will be based on Full Analysis Set.

Tables and Descriptive Statistics

Unless specified otherwise all tables and statistics will be presented using the FAS.

Evaluation of DLT will not be based on FAS but on DLT Analysis Set.

Unless specified otherwise summary tables and figures will be presented by dose regimen (Q1W or Q2W), dose group, and visit (where applicable); also, overall summaries will be shown for the two-dosage regimen and for all patients pooled together. In general, summary tables will be structured in three parts: first part will summarize overall results obtained in the two dose regimens Q1W, Q2W and in all patients pooled together; second part will display all dose groups within the dosage regimen Q1W; third part will display all dose groups within the dosage regimen Q2W.

In general, for variables showing multiple possible categories, these will be displayed with following the within variable logic criteria, for example: ECOG categories will be displayed from 0 and going to grow; where such a logic criterium does not exist (example: gender, ethnicity, SOC, PT), categories will be displayed by descending frequencies based on the overall all patients pooled together. In the end, the order used to show categories within variables should be the same in the three parts of each table.

Unless otherwise stated, continuous data will be summarized using descriptive statistics including: number of non-missing observations (n), arithmetic mean, standard deviation (SD), median, minimum, and maximum.

Categorical data will be summarized in terms of the number of patients providing data at the relevant time point (n), frequency counts and percentages. Any planned collapsing of categories will be detailed in the SAP text and the data displays. Percentages will be calculated using n as the denominator. Changes from baseline in categorical data will be summarized using shift tables where appropriate.

PAREXEL International
Statistical Analysis Plan Template for Early Phase Studies

Symphogen A/S
Sym013-01

The following rules will apply to all descriptive statistic displays, except the PK concentrations and parameters that are reported in significant digits described in section 4.10.4.4 below, where d denotes the decimal places in the original reported value:

- n : 0 decimal places (d.p.)
- Mean: $d + 1$ d.p.
- Confidence Interval: $d + 1$ d.p.
- SD: $d + 2$ d.p.
- Median: $d + 1$ d.p..
- Minimum: d .
- Maximum: d .
- Statistics in percentage: 1 d.p.
- p-value: 4 d.p.
- Except for p-value, a maximum of 3 decimal places will be displayed.

P-values greater than or equal to 0.001, in general, will be presented to three decimal places. P-values less than 0.001 will be presented as “<0.001”.

Details for reporting of statistical summaries specific to PK are detailed in section 4.10.1.4.

Figures

If not otherwise specified, each figure will be presented separately for the two dose regimens (Q1W and Q2W) with differentiate legend to discriminate the dose groups within the regimen; moreover, an overall figure will also be presented with differentiate legend to discriminate the two dose regimens. In the end, there will be three panel for each figure: first panel will show all patients, second panel patients in Q1W regimen, third panel patients in Q2W regimen.

All figures will be produced in black and white.

PAREXEL International
Statistical Analysis Plan Template for Early Phase Studies

Symphogen A/S
Sym013-01

Specification for PK figures will be detailed in section 4.10.4.1.

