4.11.7 Vital Signs and Body Measurements

Data for vital signs (body weight, blood pressure, heart rate, temperature) will be listed by part, dose group, patient, at Baseline and EOT.

PAREXEL International
Statistical Analysis Plan Template for Early Phase Studies

Symphogen A/S
Sym013-01

Descriptive summary statistics (for observed values and changes from baseline) for vital sign parameters (blood pressure and heart rate) will be provided for Baseline, EOT and Worst Result post Baseline (i.e. Maximum and Minimum post Baseline including results from unscheduled assessments) by regimen and dose group.

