4.11.8 Physical Examination

All abnormal findings from the physical exam will be listed.

A shift table from baseline to EOT and worst from baseline of normal and abnormal findings in physical examination by regimen and cohort will be produced.

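### SAP 4.2 lets a reading taken before the last infusion become the EOT value if dosing-day records are untimed and the rule is applied by date

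*SAP*

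**What the plan says.** SAP 4.2 gives the derivation used for every EOT summary. End of Treatment "is defined as the first assessment on or after the last dose of study treatment, considering both scheduled and unscheduled assessments". It mentions neither the end of the infusion nor the EOT visit. That visit is a separate event, due within 10 days of the decision to stop (SAP 3.1, overall trial plan table; Protocol 5.3.4).

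Under Baseline, the same section has one convention for records without a clock time. "Safety assessments at Cycle 1 Day 1 with no time of assessment (i.e. Vital Signs and Body Measurements, ECOG PS, Physical Examination") are taken to precede treatment. It has no counterpart for later dosing days.

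The schedule places these assessments before dosing:

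- Vital signs (SAP 3.2.4.6) "will be monitored at Screening, prior to each dosing, EOT, 1-month FUP and as clinically indicated".
- Physical examination after screening (SAP 3.2.4.7) is done "at Screening, Day 1 of each cycle prior to dosing, EOT, 1M FUP and as clinically indicated".
- For performance status (SAP 3.2.4.8), "ECOG PS will be assessed at Screening, Day 1 of each cycle (prior to dosing), EOT, 1M FUP and as clinically indicated".

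The derived value is then used in SAP 4.11.7 to 4.11.9. Summary statistics for vital signs "will be provided for Baseline, EOT and Worst Result post Baseline". For physical examination the plan calls for "A shift table from baseline to EOT and worst from baseline of normal and abnormal findings in physical examination by regimen and cohort", and ECOG PS has a similar shift table.

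**The concern.** The word *on* admits records from the day of the last dose. For vital signs, the only scheduled record on that day is the one taken before the infusion. A programmer comparing dates would select it, because it is the earliest record that qualifies, and would never reach the EOT visit. The column labelled EOT would then describe the patient before the last infusion, not after treatment ended.

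The SAP evidently met this problem on the baseline side, where it added a convention for untimed records, but it left the other end of treatment open. Two programmers following SAP 4.2 in good faith could produce different EOT columns. Part 1 has safety and tolerability as its primary objective, and the three tables concerned (14.3.6.1, 14.3.6.6 and 14.3.6.8) all carry the asterisk for the abbreviated CSR.

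**Working it through.** The plan gives no figure to reproduce. The check is which record the written rule selects.

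**Inputs.** The EOT rule and the untimed-record convention (SAP 4.2); assessment timing (SAP 3.2.4.6 to 3.2.4.8, in agreement with Protocol 8.2.4 to 8.2.6); dosing days and the EOT visit (SAP 3.1); scan timing (Protocol Table 2 and Table 3, footnote 11); asterisks (SAP 6).

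**Step 1: what the rule compares.** It selects the earliest record that is not before the last dose. The SAP does not say whether the comparison is by date or by clock time.

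**Step 2: apply it to the last-dose day, considering scheduled records only.**

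| Assessment | Scheduled record on the last-dose day | EOT value, clock-time reading | EOT value, date reading |
|---|---|---|---|
| Vital signs | Always, before the infusion | Next later record, normally the EOT visit | Pre-infusion record |
| ECOG PS | Only if the last dose was on Day 1 of a cycle, before the infusion | Next later record, normally the EOT visit | Pre-infusion record if Day 1; otherwise the next later record |
| Physical examination | As for ECOG PS | As for ECOG PS | As for ECOG PS |

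The clock-time reading needs a time on the record. SAP 4.2 names these three assessments as untimed at Cycle 1 Day 1. That they are also untimed on later dosing days is a reasonable inference, but the documents do not state it.

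**Step 3: how often ECOG PS and physical examination are exposed.** Q1W doses fall on Days 1, 8, 15 and 22, and Q2W doses on Days 1 and 15. Scheduled scans fall in the week before Day 1 of the next cycle. A patient stopped for progression at such a scan would usually have had the last dose on Day 22 (Q1W) or Day 15 (Q2W), not on Day 1. The number exposed cannot be estimated from the documents and is probably small.

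**Step 4: what is not touched.** Worst-post-baseline results, adverse events and DLTs do not use the EOT definition. ECG and ECHO/MUGA are scheduled only at screening and EOT, so they are largely unaffected. Laboratory samples are also drawn before dosing, but SAP 4.2 does not name them among the untimed records, so this point does not extend to them.

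**The case against.** The strongest reply is that the SAP already fixes the order of events by schedule. SAP 3.2.4.6 to 3.2.4.8 put the dosing-day assessments before the dose and name EOT as a separate timepoint. A scheduled dosing-day record is therefore known to be pre-dose without a clock time, and *on* can be kept for post-infusion readings that day, such as unscheduled ones. This is fair, and a careful programmer might work that way. But no text says to do so, and the only explicit convention stops at Cycle 1 Day 1.

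A second reply concerns patients dosed only on Cycle 1 Day 1. A reader might infer that one record would serve as both Baseline and EOT, giving a vital-sign change of zero by construction. The documents argue against that. SAP 4.2 already rules the untimed Cycle 1 Day 1 record pre-treatment, and for such a patient the first and last doses are the same event. Calling that record *on or after* the dose would mean setting the SAP's own ruling aside. An explicit statement would help, but no affected patients should be counted on this ground.

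Third, a reader might infer that the EOT-visit vital signs would disappear from the report. Listing 16.2.9.1 (vital signs) is asterisked, and SAP 4.2 says that listings hold all scheduled and unscheduled measurements, so the values should be visible. Some doubt remains because SAP 4.11.7 says the vital-sign data "will be listed by part, dose group, patient, at Baseline and EOT". ECOG PS Listing 16.2.9.5 is also asterisked; physical examination Listing 16.2.9.4 is not.

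Finally, the analyses are descriptive, with no hypothesis test, in a trial stopped during Part 1. That stands, and it sets the severity.

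**Conclusion.** The gap is real, conditional and minor. It rests on two assumptions: that vital signs, ECOG PS and physical examination are untimed on dosing days after Cycle 1 Day 1, and that the rule is applied by date. If both hold, the EOT vital signs in Table 14.3.6.1 are pre-infusion values for nearly every patient, and Tables 14.3.6.6 and 14.3.6.8 mix pre-infusion and post-treatment values for what is probably a small number. If either fails, the current wording selects a post-infusion record.

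Two stronger statements should be avoided. A reader might conclude that the EOT column will be wrong; the documents show only that the rule permits it. A reader might also put a ceiling on how far the selected value precedes the EOT visit by adding the dosing interval to the 10-day visit window: 7 + 10 = 17 days for Q1W and 14 + 10 = 24 days for Q2W. Those sums assume that the stop is decided exactly when the next dose is due. Protocol 7.1.4.2 delays dosing until the retreatment criteria are met, and Protocol 9.5.1 contemplates delays of more than 2 weeks, so they are not maxima.

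**What to change.** In SAP 4.2:

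1. Define EOT as the first assessment, scheduled or unscheduled, after the last infusion.
2. Extend the Cycle 1 Day 1 convention: untimed scheduled assessments on any dosing day are treated as pre-dose and cannot serve as EOT. This also settles the position for patients dosed only on Cycle 1 Day 1.
3. Flag EOT values taken from the one-month follow-up visit.

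The cost is two or three sentences and one programming rule. The downside is that a few EOT values will be missing or will come from the follow-up visit, 30 to 37 days after the last dose (30 + 7 = 37). The current rule already falls back to that visit when no earlier qualifying record exists.

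Giving the EOT visit priority over an earlier post-infusion assessment is optional. It would change the definition beyond what this point needs, because it would pass over unscheduled post-infusion readings that the SAP now selects.
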